### **6.2. Secondary Endpoint**

#### **6.2.1. Substudy A Secondary Immunogenicity Endpoint**

RSV A– and RSV B–neutralizing antibody titers will be summarized for each of the 2 vaccine groups ([Section 2.2.2.1.1](#)).

##### **6.2.1.1. Main Analysis**

- Estimand strategy: Hypothetical approach ([Section 2.2.2.1.1](#)).
- Intercurrent events and missing data: All data collected after or at intercurrent events will not be included; missing data will not be imputed.
- Analysis set: Evaluable immunogenicity population ([Section 4](#)).
- Analysis timing: At primary analyses (when all primary endpoint data are available). If the 6-month postvaccination data are available after the primary analysis, the data will be summarized after the primary analysis with all-time points presented.
- Analysis methodology: 95% CIs of GMTs and GMFRs ([Section 5.2.2](#)).
- Descriptive statistics, including sample size (n), RSV A NT, RSV B NT, and RSV A/B NT GMTs and GMFRs, and 95% CIs for GMTs and GMFRs at each applicable visit, will be presented for each vaccine group ([Section 5.2.2](#)).

##### **6.2.1.2. Supplementary Analysis**

To support the assessment of immunogenicity, estimands as specified in [Section 2.2.3](#), using the treatment policy strategy, may be summarized with the mITT immunogenicity population using the same presentation as specified in the main analysis, without the RCDCs.

### **6.3. Other Endpoint**

#### **6.3.1. Substudy B Other Immunogenicity Endpoint**

The rate of RSV A NT seroresponse and the rate of RSV B NT seroresponse after each dose will be descriptively summarized for participants in Substudy B.

## 6.4. Subset Analyses

For Substudy A, all immunogenicity results will be summarized by age (18 through 49 years of age and 50 through 59 years of age), sex, race, ethnicity, and prespecified medical condition groups (defined in [Section 3.4.2](#)). The NT GMTs/GMFRs for these subgroup analyses will be applied to the participants who received RSVpreF.

For Substudy B, the primary endpoints will also be analyzed for the 2 age groups ( $\geq 18$  to  $< 60$  years of age and  $\geq 60$  years of age). Additionally, primary immunogenicity will be summarized for each of the 4 immunocompromised groups ([Section 3.4.2](#)), and by race, ethnicity, and sex.

## 6.5. Baseline and Other Summaries and Analyses

Data will be summarized for Substudy A and Substudy B, separately. Substudy A data will be summarized for each of the 2 vaccine groups, and Substudy B data will be summarized for each of the 2 age groups ( $\geq 18$  to  $< 60$  years of age and  $\geq 60$  years of age).

### 6.5.1. Baseline Summaries

For each vaccine group or each age group, descriptive summary statistics for demographic characteristics (age at vaccination, sex, race, ethnicity, and tobacco use) will be generated, as well as for all participants in total, based on the safety population. The medical conditions for Substudy A and the immunocompromised groups for Substudy B will also be summarized for the demographic characteristics. Summary data will also be presented for the evaluable immunogenicity population.

Participant data listings for demography and baseline characteristics will also be generated.

### 6.5.2. Study Conduct and Participant Disposition

The number and proportion of randomized participants will be included in the participant disposition summary. In addition, vaccinated participants who completed the 6-month follow-up visit, and who withdrew before the follow-up visit, along with the reasons for withdrawal, will be tabulated by vaccine group (for Substudy A) or by age group (for Substudy B) and for all participants. In addition, for Substudy B, the total number of participants vaccinated at each dose, and withdrawn after each dose, will also be tabulated. The reasons for withdrawal will be those as specified in the database.

Participants excluded from the evaluable and mITT populations will also be summarized with reasons for exclusion.

The e-diary completion rate will be summarized for the safety population, by vaccine group, as well as summarized with the categorized days specified in [Section 3.4.3](#).

Standard listings will all be generated, including, but not limited to, participants who withdrew during the study, participants excluded from analysis populations, and participants with major protocol violations.

### 6.5.3. Nonstudy Vaccines

Nonstudy vaccines recorded from 28 days prior to study enrollment through the end of the study will be categorized according to the WHO Drug Dictionary and may be summarized by vaccine group for Substudy A and by age group for Substudy B, and for all participants included in the safety population.

A listing may be used to replace the table.

## 6.6. Safety Summaries and Analyses

### 6.6.1. Adverse Events

For all of the AEs categorized in [Section 3.1.3.3](#), each individual AE will be categorized by MedDRA and descriptively summarized by vaccine group.

A 3-tier approach will be used to summarize AEs. Under this approach, AEs are classified into 1 of 3 tiers ([Section 3.5.2](#)). For both Tier 1 and Tier 2 events, 2-sided 95% CIs, for the difference between the active vaccine and placebo groups in the percentage of participants reporting the events based on the Miettinen and Nurminen method, will be provided. In addition, for Tier 1 events, the asymptotic p-values will also be presented for the difference between groups in the percentage of participants reporting the events, based on the same test statistic and under the assumption that the test statistic is asymptotically normally distributed. AE displays will be sorted in descending order of point estimates of risk difference within the SOC. For Substudy A, the analysis of Tier 1 events is planned for comparing the RSVpreF vaccination group and the placebo vaccination group. For Substudy B, the analysis of Tier 1 events will be compared with the background rate that had similar population characteristics, considering no placebo group was included in Substudy B.

It should be recognized that most studies are not designed to reliably demonstrate a causal relationship between the use of a pharmaceutical product and an AE or a group of AEs. Except for select events in unique situations, studies do not employ formal adjudication procedures for the purpose of event classification. As such, safety analysis is generally considered an exploratory analysis and its purpose is to generate hypotheses for further investigation. The 3-tier approach facilitates this exploratory analysis.

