8.4.8. Adverse Events of Special Interest

The following events are considered AESIs in Substudy A and Substudy B:

- Diagnosis of Guillain-Barre syndrome
- Diagnosis of acute polyneuropathy without an underlying etiology
- Diagnosis of atrial fibrillation
- Preterm delivery (delivery at <37 0/7 weeks' gestation)
- Diagnosis of a hypertensive disorder of pregnancy

Details of the AESIs listed above are further defined in the investigator site file.

All AESIs must be reported as an AE or SAE following the procedures described in Sections [8.4.1](#) through [8.4.4](#) from the time the participant provides informed consent through the end of study participation. An AESI is to be recorded as an AE or SAE on the CRF. In addition, an AESI that is also an SAE must be reported via PSSA or using the Vaccine SAE Report Form.

AESIs are examined as part of routine safety data review procedures throughout the clinical trial and as part of signal detection processes. Should an aggregate analysis indicate that these prespecified events occur more frequently than expected, eg, based on epidemiological data, literature, or other data, then this will be submitted and reported in accordance with Pfizer's safety reporting requirements. Aggregate analyses of safety data will be performed on a regular basis per internal SOPs.

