9. STATISTICAL CONSIDERATIONS

Methodology for summary and statistical analyses of the data collected in this study is described here and further detailed in the SAP, which will be maintained by the sponsor. The SAP may modify what is outlined in the protocol where appropriate; however, any major modifications of the primary endpoint definitions or their analyses will also be reflected in a protocol amendment.

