10.8.9.3.2. Primary Endpoint(s)/Estimand(s) Analysis

Table 8. Primary Endpoint Analyses

Endpoint	Statistical Analysis Methods
Safety	
 • Descriptive statistics will be provided for each reactogenicity endpoint. Local reactions (redness, swelling and pain at the injection site) and systemic events (fever, nausea, fatigue, headache, vomiting, diarrhea, muscle pain, and joint pain) from Day 1 through Day 7 after each vaccination will be presented by maximum severity and any severity. Descriptive summary statistics will include counts and percentages of participants with the indicated endpoint and the associated Clopper-Pearson 95% CIs (Section 9.3.1.1).

Table 8. Primary Endpoint Analyses

Endpoint	Statistical Analysis Methods
	
• AEs and SAEs will be categorized according to MedDRA terms. All of the AEs within 1 month after each vaccination and the AESIs, SAEs, and NDCMCs throughout the study will be descriptively summarized with counts, percentages, and associated Clopper-Pearson 95% CIs (Section 9.3.1.1).• A 3-tier approach will be used to summarize AEs. (1) Tier 1 events are prespecified events of clinical importance and are identified in a list in the product's safety review plan and described in detail in the SAP. (2) Tier 2 events are considered "relatively common" events; a MedDRA PT is defined as a Tier 2 event if there are at least 1% of participants in any vaccine group reporting the event, in any age stratum. As there is no placebo group in this substudy, Tier 2 event analysis is not defined. (3) Tier 3 events are those that are neither Tier 1 nor Tier 2 events.• For Tier 1 events, the 95% CIs for the difference in the percentage of participants reporting the events between the RSVpreF group from this substudy and a control will be calculated using the test statistic proposed by Miettinen and Nurminen. In addition, for Tier 1 events, the asymptotic p-values will be presented for the difference between groups in the percentage of participants reporting the events, based on the same test statistic and under the assumption that the test statistic is asymptotically normally distributed. The control will be defined in the SAP.

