### 2.1. Modifications to the Analysis Plan Described in the Protocol

There is no change in analysis from the plan specified in the protocol.

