### **3.5.2. Adverse Events**

A 3-tier approach will be used to summarize AEs. Under this approach, AEs are classified into 1 of 3 tiers. Different analyses will be performed for different tiers (refer to [Section 6.6.1](#)).

- Tier 1 events: These are prespecified events of clinical importance and are maintained in a list in the product's safety review plan. Guillain-Barre syndrome, acute polyneuropathy, atrial fibrillation (occurring from vaccination through the 1-month follow-up visit), preterm delivery (occurring from vaccination through the end of the study), preterm birth (occurring from vaccination through the end of the study), and hypertensive disorders of pregnancy (occurring from vaccination through the end of the study) will be included as the Tier 1 event analysis for RSVpreF. The derivation for Guillain-Barre syndrome and acute polyneuropathy is from Day 1 through Day 43 after vaccination (Day 1 is the vaccination day) for Substudy A and is from Day 1 of initial vaccination through Day 43 of the last vaccination for Substudy B. The RSV program Tier 1 list of MedDRA PTs is maintained by the safety risk lead in the CAETeLiSt and is

referenced in the safety surveillance review plan for the program. The current list of Tier 1 events referenced by this study for RSVpreF should be confirmed to ensure that appropriate Tier 1 events will be used to produce final tables/graphs before conducting an analysis.

Note that the denominator for calculating the preterm delivery, preterm birth, and hypertensive disorders of pregnancy would be the number of pregnant women in the corresponding substudy.

- Tier 2 events: These are events that are not Tier 1 but are “common.” A MedDRA PT is defined as a Tier 2 event if its incidence is at least 1% in any study intervention group. As there is no placebo group in Substudy B, Tier 2 event analysis is not defined for this substudy.
- Tier 3 events: These are events that are neither Tier 1 nor Tier 2 events.

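### Substudy B Tier 1 events: the protocol's two-sample Miettinen-Nurminen analysis has no defined comparator in the SAP, and its asymptotic p-value is unreliable for very rare events even once one is supplied

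*SAP*

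**What the plan says.** Protocol 10.8.9.3.2 (Table 8) sets the Substudy B method for Tier 1 events. A 95% CI for the difference in percentages "between the RSVpreF group from this substudy and a control will be calculated using the test statistic proposed by Miettinen and Nurminen". An asymptotic normal p-value from the same statistic is added, and then: "The control will be defined in the SAP".

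SAP 6.6.1 describes the Miettinen-Nurminen interval as "for the difference between the active vaccine and placebo groups in the percentage of participants reporting the events". For Substudy B, which has no placebo group, it says: "For Substudy B, the analysis of Tier 1 events will be compared with the background rate that had similar population characteristics". It gives no source, rate, event count or denominator. SAP 5.2.1 describes the method for differences between vaccine groups, and the SAP contains no one-sample method against a fixed rate. Protocol section 9 allows that "The SAP may modify what is outlined in the protocol where appropriate", but SAP 2.1 states: "There is no change in analysis from the plan specified in the protocol".

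Other parts are settled. SAP 3.5.2 gives event windows; for Guillain-Barre syndrome and acute polyneuropathy the window "is from Day 1 of initial vaccination through Day 43 of the last vaccination for Substudy B". It also sets the number of pregnant women as the denominator for pregnancy events. Protocol 10.8.9.1 calls Substudy B descriptive and says that it tests no hypothesis.

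**The concern.** The protocol hands one task to the SAP, defining the control, and the SAP answers with a phrase that could mean a single published rate or a cohort with its own count and size. These need different analyses, and the only method on the page suits the second.

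The stated p-value is also a poor tool here. Tier 1 events are the prespecified events of clinical importance. Some are likely to produce no case or one case in about 200 vaccinees, where a normal approximation is weakest. SAP 7.1.1 lets open-label Substudy B data be summarised on an ongoing basis, so a comparator could be picked after a case is known. A single chance case could then carry an extreme p-value that the data do not justify, in a substudy described as having no hypothesis tests.

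**Working it through.** **Inputs.** n1 = 200 (Protocol 1.1, approximate). Two-sided 95% level (SAP 5.2). The plan states no rate, comparator size or p-value for this analysis, so there is no figure to reproduce. All background risks and comparator sizes below are assumptions, shown as ranges.

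**Statistic at difference 0.** With N = n1 + n2 and p = (x1 + x2)/N,

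z = (x1/n1 − x2/n2) / √[ p(1−p)(1/n1 + 1/n2) · N/(N−1) ].

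This needs x2 and n2, and a bare rate supplies neither. With one event against none, it reduces to z = √(n2/n1). With no events in either group it is 0/0, so the p-value is undefined.

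**One case in 200 against assumed comparators**

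| Comparator | z | Asymptotic p | Fisher p | 95% CI, percentage points |
|---|---|---|---|---|
| 0/200 | √1 = 1.00 | 0.32 | 1.0 | −1.39 to 2.78 |
| 0/1,000 | √5 = 2.24 | 0.025 | 0.17 | 0.09 to 2.78 |
| 1/10,000 | 4.90 | 1e-6 | 0.039 | 0.08 to 2.77 |
| 10/100,000 | 6.61 | 4e-11 | 0.022 | 0.08 to 2.77 |

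Worked line for the last row: p = 11/100,200 = 1.098e-4; variance ≈ 1.098e-4 × 0.00501 = 5.50e-7; z = (0.0050 − 0.0001)/7.42e-4 = 6.61.

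The last two rows have the same observed background rate and the same interval to two decimals. The asymptotic p-value falls by more than four orders of magnitude while Fisher's barely moves. The fault is therefore mainly in the p-value.

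Size is not the only driver. At a fixed n2 of 100,000, comparator counts of 10, 50 and 100 give p = 4e-11, 0.005 and 0.075.

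**If the rate is treated as exactly known.** The limit of the statistic is a one-sample score test, which the documents do not specify. At risk 1e-4, z = (0.005 − 0.0001)/√(1e-4 × 0.9999/200) = 6.93, p = 4e-12. The exact chance of one or more cases is 1 − 0.9999^200 = 0.0198.

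**True size at nominal 5%.** Sum of Binomial(200, r) × Binomial(n2, r) probabilities over tables with p < 0.05, for n2 = 200, 500, 1,000, 2,000, 5,000, 10,000, 20,000, 50,000 and 100,000.

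| Background r | Size across n2 |
|---|---|
| 1e-4 | 0 to 2.0% |
| 5e-4 | 0 to 9.5% |
| 8e-4 | 0 to 12.1% |
| 1e-3 | 0.01 to 8.3% |
| 5e-3 | 1.4 to 6.0% |
| 1e-2 | 3.8 to 5.1% |

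At 8e-4 the sizes in order of n2 are 0.0, 0.8, 7.1, 8.3, 7.1, 9.2, 8.9, 10.9 and 12.1%. At 1e-4 the flag is not inflated; only the size of the p-value misleads.

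**A commoner event.** For 8/200 against an assumed 2% control, p = 0.24, 0.087, 0.048 and 0.044 for n2 = 200, 1,000, 10,000 and 100,000. This settles as the comparator grows.

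**Check of an observed/expected alternative.** The exact Poisson 95% CI for one event is 0.0253 to 5.572, divided by the expected count. With no vaccine effect and a known rate, it excludes 1 in 2.0, 0.5, 1.2, 1.8, 1.9 and 1.7% of cases at the six rates above. If the expected count is instead estimated from a sampled background (zero expected with at least one case counted as exclusion):

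- r = 1e-3: 14.9% at n2 = 200, 7.3% at 1,000, about 1.5% at 5,000.
- r = 5e-3: 24.6% at n2 = 200.

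If the true rate is 2 or 5 times an assumed 1e-3, false exclusion is 6.2% or 26%.

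**The case against.** A background described as having similar population characteristics may well be a cohort with a count and a denominator, and then the planned statistic can be run. The Substudy B method is not missing either. Table 8 states it, SAP 2.1 keeps it, and the p-value sentence in SAP 6.6.1 speaks of groups in general. Both points stand. A reader might infer that the analysis is impossible as written, but the documents support that only for a bare rate. What is missing is the comparator.

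All rates and sizes above are assumed, and the documents place no Tier 1 event in the band where error is inflated. With no cases in Substudy B, the p-value is undefined or non-significant. This also stands, and it limits the claim to what could happen if a rare event occurs.

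The safety reading is also cushioned. SAP 6.6.1 calls safety analysis generally exploratory. Adverse events of special interest already receive Clopper-Pearson intervals. Protocol 8.4.8 already has routine review ask whether "these prespecified events occur more frequently than expected, eg, based on epidemiological data, literature, or other data". This lowers the stakes, but it does not define the promised control or make the planned p-value reliable.

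**Conclusion.** The point holds as a minor specification gap combined with an unsuitable p-value. The protocol's control is not defined in the SAP. If it is a bare rate, the two-sample statistic is undefined. If it is a cohort, the asymptotic p-value for a very rare event in about 200 vaccinees depends heavily on the cohort's size and observed rate, and can be many orders of magnitude smaller than an exact one. Planning p-values also sits badly with Protocol 10.8.9.1.

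Two stronger readings are tempting and are not supported:

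- **That Tier 1 testing in Substudy B is anticonservative in general.** Size clearly exceeds 5% only at assumed backgrounds of roughly 5e-4 to 1e-3 with comparators of 1,000 or more. It is at most 2.0% at 1e-4 and at most 5.1% at 1e-2. Nothing in the documents shows atrial fibrillation to be rare enough to be affected.
- **That comparator size alone drives the result.** The comparator's observed rate matters as well.

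No trial conclusion depends on this analysis.

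**What to change.** In Protocol Table 8 and SAP 6.6.1, for Substudy B Tier 1 events:

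1. Drop the asymptotic p-value, or replace it with an exact one.
2. With an external rate from a large source, report observed and expected numbers of participants with the event in its SAP 3.5.2 window. Expected is the sum over participants of background incidence × actual time in the window. Give the ratio with an exact Poisson 95% CI and a sensitivity range for the assumed rate.
3. With a sampled control, report its count and N and use an exact two-sample method that carries its sampling error.
4. List pregnancy events with the number of pregnant women and an exact CI.
5. Fix the source and rate for each event before any Substudy B safety summary, and record the change in SAP 2.1.

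**Limits.** The Poisson interval holds its nominal error only if the background rate is correct and precisely estimated. With a small source (for example N = 200 to 1,000), or a true rate 2 to 5 times the assumed one, false exclusion can exceed 5%, as shown above. Chance signals also remain. One case still excludes 1 when fewer than 0.0253 events are expected, that is, at a background below 0.0253/200 ≈ 1.3e-4. One case against 0.02 expected gives a ratio of 50 (1.27 to 279); against 0.1 it gives 10 (0.25 to 56).

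**Cost.** Wording in Table 8 and SAP 6.6.1 and 2.1, plus one sourced rate per event. No new trial data.

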## 7. INTERIM ANALYSES

No interim analysis is planned.

### 7.1. Introduction

#### 7.1.1. Analysis Timing

For Substudy A, when all primary safety endpoint and primary immunogenicity endpoint data become available, it will be unblinded for the primary analysis. All safety data collected throughout the study will be cleaned, and primary and secondary immunogenicity data through 1 month after vaccination will also be cleaned and included in the analysis, with all type I error spent in this primary analysis.

For Substudy B, as it is open-label, data may be summarized on an ongoing basis for decision-making. Final analysis will be performed when all data are available and cleaned for analysis.

## 9. APPENDICES

### Appendix 1. List of Abbreviations

Abbreviation	Term
AE	adverse event
AESI	adverse event of special interest
ANCOVA	analysis of covariance
BLQ	below the limit of quantitation
CAD	coronary artery disease
CAETeLiSt	Custom Adverse Event Term List System
CBER	Center for Biologics Evaluation and Research (United States)
CHF	congestive heart failure
CI	confidence interval
COPD	chronic obstructive pulmonary disease
CRF	case report form
e-diary	electronic diary
FDA	Food and Drug Administration (United States)
GMFR	geometric mean fold rise
GMR	geometric mean ratio
GMT	geometric mean titer
ICD	informed consent document
IRT	interactive response technology
LLOQ	lower limit of quantitation
LS	least square
MCAR	missing completely at random
MedDRA	Medical Dictionary for Regulatory Activities
MITT	modified intent-to-treat
N/A	not applicable
NDCMC	newly diagnosed chronic medical condition
NSCLC	non–small-cell lung cancer
NT	neutralizing titer
PT	preferred term
QNS	quantity not sufficient
RCDC	reverse cumulative distribution curve
RSV	respiratory syncytial virus
RSV A	respiratory syncytial virus subgroup A
RSV B	respiratory syncytial virus subgroup B
RSVpreF	respiratory syncytial virus stabilized prefusion F subunit vaccine
SAE	serious adverse event
SAP	statistical analysis plan
SOC	system organ class
SOT	solid organ transplant
WHODrug Dictionary	World Health Organization Drug Dictionary

